2.1 STUDY DESIGN

This is a non-interventional study. This study NOT designated as a Post- Authorizations Safety Study (PASS).

[figure not shown]
2.1.1 General overview of the NIRVANA project.

This protocol use a primary source FFPE biopsies and clinical records obtained from patients recruited in clinical sites distributed in Chile, Brazil, and Peru. The FFPE is used to evaluate the ALK biomarker using either Vysis ALK Break Apart FISH test or the Ventana ALK IHC test and to perform the Next generation sequencing in nucleotides prepared from NSCLC FFPE blocks.

090177e191f145b5\Approved\Approved On: 25-Sep-2019 09:10 (GMT)

2.1.2 General overview of NGS test.

Prior to performing the NGS Test, the FFPE clinical specimens are prepared for pathology review. A microtome is used to prepare 5µm FFPE sections. A 5µm FFPE section is stained using a standard hematoxylin and eosin (H&E) protocol. Stained tissue sections are visually examined by a pathologist for confirmation of tumor content area, tumor content per tissue section (TC), region(s) of interest (ROI), ROI tumor content (ROI TC), and percent necrosis are all recorded on the case report form (as described in Protocol N° X9001083). If tumor content is greater than or equal to 20%, the tissue sections will be extracted. If tumor content is less than 20%, and ROI is greater than or equal to 10%, tumor areas will be macrodissected and enriched for tumor, in preparation for the extraction protocol.

Two sections will be extracted in order to meet minimum tissue input requirements. The tissue (with or without macrodissection) is taken through sample processing to isolate gDNA and total cell RNA. cDNA prepared from Total RNA is

The prepared DNA or cDNA sample is made into a library of amplicons using the Ion PGM Library Kit. Each sample is given a unique, identifying sequence by the addition of a nucleic acid barcode adapter. Using these barcode adapters up to 6 specimens (1 DNA library and 1 RNA library from each sample) each with its own unique barcode can be templated and sequenced in the same system run with DNA, RNA and 2 NTC Controls.

The libraries are templated onto Ion Sphere Particles (ISP, which are proprietary beads) using the Ion OneTouch Template Kit and OneTouch instrument. Templated beads are enriched from un-templated beads on the OneTouch ES, and loaded onto the 318 chip with reagents to allow the sequencing reactions to take place.

The Ion PGM Sequencer uses the reagents provided in the Ion PGM Sequencing Kit to detect nucleotide incorporation on the chip. The signal generated by the sequencing reaction on the 318 chip is translated into base calls and then reads. The DNA reads are 'mapped' to the reference human genome (hg19) followed by detection of SNVs, Indels, and CNVs.

The RNA reads are 'mapped' to a reference containing control sequences and candidate gene fusion sequences. Gene fusions are detected as present if they map to these sequences and pass certain filtering criteria.

The end result of this workflow is a set of variant calls that correspond to the original sample. The Ion PGM Torrent Suite software will call out any variation between the Reproducibility Sample member sequence at the locations designated in the Hot Spot file. This process is executed using the Ion PGM Torrent Suite software which runs on the Ion Torrent Server. The Ion PGM Torrent Suite software manages the complete end-to-end workflow from sample to variant call.

The clinical data will be recorded in an electronic case report form (eCRF) managed digitally in the platform Medsharing. This system allows tracking and controlling the clinical

information associated to the specimen. It is based in an online interface that allows the centralized management of multiple clinical sites.

Study population

The study population includes all patients who satisfy all inclusion and do not present any of the exclusion criteria detailed in the protocol.

Inclusion Criteria (according with amendment 2, 23 November 2017)

- 1. Men or women 18 years of age or older.*
- 2. Patients with a diagnosis of non-small cell carcinoma (NSCLC) histologically or cytologically tested.*
- 3. When a blood sample is donated, the individual must have an active tumor, i.e. the patient has a tumor in the moment of blood collection. The diagnosed is based on image test i.e.: X- RAY, Ct SCAN, RMN, PET Scan and among other, and biopsy (liquid or standard).*
- 4. Informed consent form, signed and dated, stating that the patient (or the legal representative) has been informed of all relevant aspects of the clinical study before being incorporated into the study, when appropriate.*
- 5. Patients must give consent for the research use of their tissues on file or fresh or 2 tubes of blood if available, or both.*

Exclusion criteria

Patients who meet some of the following criteria will not be included in the study:

- 1. Previous chemotherapeutic treatment in the last six weeks before taking the sample (tumor tissue or blood or both)*
- 2. Bone biopsy of non-small cell carcinoma (NSCLC)*
- 3. Biopsy taken no longer than two years old*

The information collected in this will be related exclusively to the period time of diagnose of the patient.

Data source

The data sources for this study include:

- 1) Medical records AND Patient interviews information stored in Medsharing server.*
- 2) Molecular profiling obtained from NGS test, storage in the CEMP servers.*

Treatment/cohort labels

No treatments are applied in this study. However, patients will be grouped base on their type of cancer, age, Ventana ALK test results and other variables described in their medical records. The objective of grouping the patients is to obtain the epidemiologic characteristics of NSCLC in the South American population. In particular the classification of patients between Ventana ALK positive vs negative will be used to make the statistical analysis to assess the agreement between NGS and Ventana ALK.

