5.1 FULL ANALYSIS SET

The final study population will include any NSCLC patients who satisfy all inclusion and exclusion criteria.

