5.4 SUBGROUPS

- The patients will be considered **RETROSPECTIVE** in those whose sample was taken before the date of signature of the IC. Meanwhile, patients whose samples were taken after the IC will be called **PROSPECTIVE**
- Based on their smoking habits, patients will be grouped into smoker or no-smokers.
- Subgroups will be considered depending on the characteristics of the samples concerning the location of the tumors, their stage and the histological classification of the biopsy.
- Different subgroups will be considered according to their gender (female/male) and different age ranges (18-30 / 31-40 / 41-60 / 60 and more).

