6 ENDPOINTS AND COVARIATES

a. Primary Endpoint.

- **Primary endpoint 1:** Obtaining results / diagnosis of NGS and Ventana for the ALK biomarker.
- **Primary endpoint 1:** Analysis of NGS y Ventana for ALK.

b. Secondary Endpoints

Secondary endpoint 1: PE1 in prospective and retrospective patients.

Secondary endpoint 2: PE1 in smokers and non-smokers.

Secondary endpoint 3: PE1 depending on the location, stage and histological classification of the biopsy

Secondary endpoint 4: PE1 in patients of different gender and age.

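### SAP exclusion criterion 3 is worded as a requirement, so read literally it excludes biopsies aged two years or less and contradicts the plan's use of tissue taken after consent

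*SAP*

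**What the plan says.** SAP section 2.1 opens its exclusion list with "Patients who meet some of the following criteria will not be included in the study". Three items follow. Item 1 concerns recent treatment: "Previous chemotherapeutic treatment in the last six weeks before taking the sample (tumor tissue or blood or both". Item 2 concerns the site from which tissue came: "Bone biopsy of non-small cell carcinoma (NSCLC". Item 3, on the age of the tissue, is worded "Biopsy taken no longer than two years old".

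The same section states how the list is to be used: "The study population includes all patients who satisfy all inclusion and do not present any of the exclusion criteria detailed in the protocol". Section 5.1 then defines the full analysis set: "The final study population will include any NSCLC patients who satisfy all inclusion and exclusion criteria".

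Other parts of the plan expect recent tissue. Inclusion criterion 5 in SAP section 2.1 accepts tissue that is on file or fresh, two tubes of blood, or both. Section 5.4 separates retrospective from prospective patients by whether the sample came before or after consent: "patients whose samples were taken after the IC will be called" prospective. Section 6 plans an analysis on that split: "Secondary endpoint 1: PE1 in prospective and retrospective patients". Section 6.4 lists the same split as a stratum to be reported. Protocol section 7 provides for archival or prospective tumour tissue.

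The supplied protocol (section 7.1.2) has a single exclusion, prior chemotherapy, and no limit on biopsy age. The SAP attributes its inclusion list to amendment 2 of 23 November 2017, whose text is not among the documents.

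**The concern.** Items 1 and 2 describe something that disqualifies a patient. Item 3 reads like something a patient must have. Placed in an exclusion list, it works in the opposite direction from the one its phrasing suggests.

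This is an operative rule. The study population and the full analysis set are defined through these criteria, and the ALK and ROS1 prevalence estimates and the comparison of NGS with Ventana ALK are computed on that population. An analyst who builds the set from the SAP text alone would keep the older blocks and drop the newer ones. The results would then describe older archival material, and secondary endpoint 1 would lose its prospective tissue patients.

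**Working it through.** The plan gives no figure on this point and no formula applies. The check applies the rule to each kind of patient and compares the outcome with the rest of the plan.

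**Direction of the list.** The lead-in speaks of patients who meet some of the items. The population statement in section 2.1 requires that none of the exclusion criteria be present, so meeting item 3 alone is enough to be left out.

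**Outcome by type of patient under the literal text.**

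| Patient | Item 3 as written | What the rest of the plan expects |
|---|---|---|
| Tissue biopsy aged two years or less | Excluded | Recent tissue is accepted (inclusion criterion 5) |
| Tissue biopsy aged more than two years | Kept | Nothing else in either document sets an age limit |
| Tissue taken after consent, age counted at enrolment | Excluded, since the tissue is days or weeks old | Prospective subgroup (5.4), secondary endpoint 1 (6), reported stratum (6.4), prospective tissue (protocol section 7) |
| Blood only, taken after consent | Not clearly reached by a rule on biopsy age | Allowed by inclusion criterion 5, and prospective under 5.4 |

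The third row is the direct contradiction. All tissue patients whom section 5.4 calls prospective would be removed.

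**Blood-only donors.** Section 5.4 classifies patients by when the sample was taken, not the biopsy. A blood-only donor sampled after consent, whose diagnostic biopsy is older than two years, is prospective and is not excluded. Such a donor gives no tissue to the ALK comparison, which SAP section 2.1.1 bases on FFPE material.

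**Reference date.** The SAP does not say when biopsy age is counted. The study is planned for about 48 months, which is 48 / 12 = 4 years, or twice the two-year limit. If age were counted at sequencing, a stored prospective block could pass two years, and the literal rule would then keep it. The third row therefore depends on counting age at or near enrolment.

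**The alternative reading.** SAP sections 5 and 5.1 speak of patients satisfying both the inclusion and the exclusion criteria. Treating every item as something to satisfy would make item 3 a two-year maximum. It would also make recent chemotherapy and a bone biopsy conditions of entry. No single reading makes all three items sensible.

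**Share affected.** This cannot be computed, because neither document gives a distribution of biopsy ages or the numbers of prospective and retrospective patients.

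**The case against.** The strongest reply is that nobody would apply the rule literally. Item 3 is visibly a requirement put in the wrong list, and the prospective subgroup, secondary endpoint 1 and the acceptance of fresh tissue all show that recent biopsies were wanted. The SAP also defers to criteria set out in the protocol and says that text taken from the protocol is italicised. The item may therefore have been carried over from amendment 2, and that amendment, which governs enrolment at the sites, may state the rule properly.

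Much of this stands. The probable intent can be read from the context, and a wording error is the most likely explanation. It does not remove the point. The SAP should let an independent analyst rebuild the analysis set, and the only biopsy-age rule in the supplied documents points the wrong way. The supplied protocol cannot correct it, because it has no such rule and its amendments section records none.

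A reader might go further and infer that every prospective patient was excluded, or that the prospective side of secondary endpoint 1 has no patients. The documents do not support that. It follows only for tissue taken after consent, with age counted near enrolment, and only if the text was applied literally. Nothing shows that recent biopsies were left out, or that a programmed eligibility check exists.

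**Conclusion.** The point holds as a contradiction within the SAP on a rule that defines the analysis set. As written, item 3 excludes biopsies aged two years or less and keeps older ones. Assuming literal application and biopsy age counted at or near enrolment, it would exclude all patients whose tissue was taken after consent, together with archival biopsies up to two years old. Its reach beyond post-consent tissue cannot be quantified.

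Confidence is high on what the words say and on the conflict with the other sections. On intent, a two-year maximum is the most plausible reading, but it cannot be confirmed without amendment 2. On what was done in practice, the documents are silent. The wording should be corrected; this is not evidence that the study analysed the wrong samples.

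**What to change.** Reconcile exclusion item 3 with amendment 2, inclusion criterion 5 and section 5.4. If, as the context indicates, a two-year maximum age is intended, either reword the item so that it excludes biopsies more than two years old or move it to the inclusion list as a condition to be met.

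State the date at which biopsy age is counted (for example, consent, enrolment or NGS testing) and whether the limit applies to patients who give blood only. Align sections 5 and 5.1 with section 2.1, so that patients meet all inclusion criteria and none of the exclusion criteria.

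Then check that the analysis set was built in the intended direction, and report the result. The cost is one line for the criterion, small alignments of wording, and one check of biopsy dates against the reference date. No new data collection is needed if those dates are on record.

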2.2 STUDY OBJECTIVES

1. To determine prevalence rate for ALK and ROS1 gene rearrangement in NSCLC patients from Latin America.
2. To determine concordance between the Ventana ALK IHC test and Thermo Fisher NGS technology.
3. To correlate the clinical data and the results from Ventana ALK and molecular diagnostics.
4. To evaluate the use of less invasive source of genomic material for the molecular classification of patients with NSCLC.

3 INTERIM ANALYSES

Given an estimated prevalence of ROS1 at 1-2% and ALK at 3-5% for NSCLC, an initial set of 1000 patients will be screened. An interim analysis will be performed at the first 1000 NSCLC samples to evaluate prevalence rates.

The first interim analysis will be carried out for the purpose of monitoring the overall progress of the study and to define the sample size of the study.

We expect that after the interim analysis changes in the final total number of recruited patient occur.

If anticipated prevalence rates do not align with determined prevalence rates at this stage, an additional 2000 patients will be screened for a potential total of 3000 patients.

A subsequent interim analysis will be performed at the 3000 NSCLC samples to evaluate prevalence rates. The main objective of this interim analysis is to determine the number of total recruited patients needed to get the statistical power.

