The endpoint of this Project will be to analyze 30 positive ROS1 and 120 positive ALK samples to validate the diagnostic method.

Given an estimated prevalence of ROS1 at 1-2% and ALK at 3-5% for NSCLC, an initial set of 1000 patients will be screened. An interim analysis will be performed at the first 1000 NSCLC samples to evaluate prevalence rates (tentatively 10 ROS1+ and 40 ALK+).

For the majority of molecular tests, it is expected that at least 50 positive patient samples be utilized for validation, and ideally at least 10 positives representing each variant being detected¹. Given the low prevalence of ROS1 which has 16 unique variants and recent analysis demonstrating that in 30 ROS1+ patient samples, there is representation of the 3 dominant variants suitable for analytical validation², it is necessary to screen at least 3000 NSCLC samples for identifying positive samples for both ROS1 and ALK that should be sufficient for analytical validation of the NGS platform. If anticipated prevalence rates at the 3000 sample mark do not align with determined prevalence rates at this stage and/or 30 positive ROS1 and 120 positive ALK samples are not obtained, an additional 3000 patients will be screened for a potential total of 6000 patients. The overall screening will occur at 3 or more sites. Patients will only participate in the study for the initial sample collection period.

The study will be completed in approximately 48 months.

Study Treatment

None.

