determined prevalence rates at this stage, an additional 3000 patients will be screened for a potential total of 6000 patients. The overall screening will occur at 3 or more sites. Patients will only participate in the study for the initial sample collection period.

The study will be completed in approximately 48 months. Since it's a non-interventional multi-center study involving the collection and analysis of FFPE tumor tissue and blood of NSCLC patients, patients will not be treated as part of the protocol.

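### Screening is extended only if observed ALK/ROS1 prevalence fails to match the expected ranges, which contradicts the plan's other sample-size rules and distorts the prevalence estimate modestly

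*SAP*

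**What the plan says.** Prevalence is the first SAP objective (2.2): "To determine prevalence rate for ALK and ROS1 gene rearrangement in NSCLC patients from Latin America". It is also the first analysis listed in SAP 8.2.

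Four places bear on how many patients are screened:

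- **SAP 3 and protocol 7.4, at 1000.** "Given an estimated prevalence of ROS1 at 1-2% and ALK at 3-5% for NSCLC, an initial set of 1000 patients will be screened". Then: "If anticipated prevalence rates do not align with determined prevalence rates at this stage, an additional 2000 patients will be screened". The SAP adds that this look is "for the purpose of monitoring the overall progress of the study and to define the sample size of the study".
- **At 3000.** Protocol 7.4 repeats the condition, now comparing the anticipated rates with the "determined prevalence rates at this stage, an additional 3000 patients will be screened for a potential total of 6000 patients". SAP 3 gives another aim for the same look: "The main objective of this interim analysis is to determine the number of total recruited patients needed to get the statistical power".
- **Protocol abstract.** "it is necessary to screen at least 3000 NSCLC samples for identifying positive samples for both ROS1 and ALK". At 3000 it keeps non-alignment as a reason to extend but adds a count condition: "and/or 30 positive ROS1 and 120 positive ALK samples are not obtained, an additional 3000 patients will be screened".
- **SAP 8.1.** The total is recalculated at each interim from a target sensitivity and the prevalence.

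No passage defines *align* or says whether both genes must align. Protocol 7.4 names the Wilson interval for sensitivity and specificity only. Neither document names an interval for prevalence or an allowance for a data-dependent sample size.

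**The concern.** Two things are at stake.

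The first is consistency. Under the literal rule in SAP 3 and protocol 7.4, matching prevalence at 1000 leaves no stated reason to continue. The abstract's minimum and counts, the SAP's power aim at 3000 and the 8.1 recalculation would each lead elsewhere. A reader cannot tell which rule sets the sample size.

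The second is the estimate. The statistic that decides whether to go on is the one that objective 1 reports. A chance result that matches the expected range is kept at a small sample, while one that does not match is diluted with 2000 or 3000 more patients. The pooled estimate is then drawn towards the expected range from either side, and an ordinary 95% interval ignores this.

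**Working it through.** **1. The plan's own counts.** Expected positives = n × prevalence. The abstract expects 10 ROS1+ and 40 ALK+ at 1000: 1000 × 1% = 10 and 1000 × 4% = 40, reproduced. At 3000: 3000 × 1% = 30 and 3000 × 4% = 120, the stated targets.

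**2. What an aligned stop delivers.**

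- At 1000: ROS1 1000 × 1–2% = 10–20 (target 30); ALK 1000 × 3–5% = 30–50 (target 120).
- At 3000: ROS1 30–60; ALK 90–150. Even here alignment can leave ALK short of 120.

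**3. What SAP 8.1 would do instead.** Positives needed = z² × SN(1 − SN)/W². The SAP gives no usable W, so W is assumed; SN = 0.8.

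- W = 0.10, z = 1.96: 3.8416 × 0.16/0.01 = 61.5.
- W = 0.10, z = 2.58: 6.6564 × 0.16/0.01 = 106.5.
- W = 0.05, z = 1.96: 3.8416 × 0.16/0.0025 = 245.9.

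Divided by 4% prevalence, these give about 1,540, 2,660 and 6,150 patients. None depends on alignment. Simulating this rule gave an ALK bias of about 0 to +0.06 percentage points, not directed to the expected range, and coverage of 94.7–95.3%.

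**4. The alignment rule, ALK alone.** Assumptions: *align* means the observed rate lies in 3–5% (limits included); looks at 1000, 3000 and 6000; pooled estimate x/n at the final n. The Wilson interval is [p̂ + z²/2n ± z√(p̂(1 − p̂)/n + z²/4n²)]/(1 + z²/n), z = 1.96. Exact binomial calculation:

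| True ALK | Bias (points) | Coverage |
|---|---|---|
| 2.0% | +0.020 | 93.5% |
| 2.5% | +0.116 | 92.6% |
| 3.0% | +0.190 | 94.8% |
| 4.0% | −0.010 | 98.5% |
| 5.5% | −0.210 | 94.9% |
| 6.0% | −0.110 | 93.6% |
| 8.0% | 0.000 | 95.2% |

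The largest biases are +0.19 near 3% and −0.25 near 5.1%. The lowest single coverage value is 91.7%, at 2.1%. For ROS1 on its own range, bias is at most about 0.16 points and the lowest single value is 91.0%. With a fixed sample, the lowest Wilson coverage over true ALK 1–9% is 93.8% (n = 1000), 94.1% (3000) and 94.5% (6000), so part of those lows is binomial discreteness.

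**5. Both genes must align.** Simulation, 1,000,000 runs, independent binomial counts, same looks:

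| True ALK / ROS1 | Non-coverage | Stop at 1000 | Mean reported, given that stop |
|---|---|---|---|
| 2.5% / 1.5% | ALK 0.073 (fixed n about 0.053) | 15% | ALK 3.24%, 18% non-coverage |
| 4% / 0.6% | ROS1 0.084 (fixed n 0.044–0.059) | 8% | ROS1 1.09%, 50% non-coverage |
| 6% / 1.5% | ALK 0.063 | 9% | ALK 4.72% |

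The two methods agree. At ALK 2.5% the ALK-only rule stops at 1000 with probability 0.18, and ROS1 at 1.5% aligns there with probability 0.85: 0.18 × 0.85 = 0.153.

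**6. First stop at 3000.**

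| True ALK / ROS1 | Gene | Alignment only | Alignment plus 30/120 counts (abstract) |
|---|---|---|---|
| 2.5% / 1.2% | ALK | 0.066 | 0.052 |
| 4% / 0.7% | ROS1 | 0.076 | 0.065 |

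**7. Counts only, first stop at 3000.** ALK 3.5% / ROS1 1.5%: ALK non-coverage 0.065. ALK 5% / ROS1 0.7%: ROS1 non-coverage 0.076. A count trigger also stops on the observed positives, so it does not restore coverage everywhere.

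**8. If *align* means that the 95% interval overlaps the range.** The coverage loss is at most about 0.01, but the mean still moves: at true ALK 6% it is 5.77%, a bias of −0.23 points.

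**The case against.** The strongest reply is that no passage orders a stop on agreement; the text says only when to extend. The abstract's minimum of 3000 rules out a stop at 1000. An aligned stop there could not meet the 30/120 targets. The milestones in protocol section 4 list reports at 1000, 3000 and 6000 without condition. SAP 3 sets the number at 3000 by power. Prevalence is not tested (SAP 4.1 confines testing to aim 2) and is not a primary or secondary endpoint in SAP 6. The re-assessment appendices are visible by title only, so the rule actually applied cannot be checked.

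Much of this stands. Stopping on agreement is an implication of SAP 3 and protocol 7.4, and other passages contradict it. Under the abstract's full rule the effect disappears in one of the two scenarios in step 6 and roughly halves in the other. But the conflict is itself the defect: the alignment wording is current text in both documents, the abstract retains it alongside the counts, and prevalence remains objective 1 with no interval specified.

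A reader might also infer that the prevalence interval under-covers whenever Latin American rates differ from the expected ones. The calculation does not support that. Under the step 4 assumptions the loss is confined to bands just outside the ranges: ALK about 1.8–2.7% and 5.6–6.6%; ROS1 about 0.4–0.9% and 2.5–3.1%. Further away coverage is nominal, and inside the ranges it is mostly conservative.

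**Conclusion.** The point holds in a limited form. The sample-size passages contradict each other, and the literal alignment rule would allow a stop that falls far short of the protocol's own counts. That part needs no simulation.

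The statistical effect on objective 1 is real but modest overall. ALK bias is at most about 0.25 percentage points, against a 95% half-width at 4% and n = 1000 of 1.96 × √(0.04 × 0.96/1000) = 1.2 points. Coverage falls about 1–3 points just outside the ranges. The serious loss is conditional on an early stop, which is uncommon in the scenarios outside the ranges (8–15% of runs), but such a study would report exactly that distorted figure.

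These sizes rest on an assumed meaning of *align* (observed rates inside both ranges), Wilson intervals and pooled estimates. Under the overlap reading the coverage loss nearly vanishes. It would be wrong to conclude that the plan certainly stops on agreement, or that a count rule alone would repair coverage. The point does not concern the ALK concordance analysis.

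**What to change.** 1. In protocol 7.4 and SAP 3, replace the alignment trigger with the abstract's minimum and counts: no stop before 3000, and extend if 30 ROS1+ and 120 ALK+ are not reached, stating that a shortfall in either gene counts. Delete the alignment clause from the abstract too, and say how the SAP 3 power aim and the 8.1 recalculation relate to this rule, so that all passages agree. Interim prevalence can be reported descriptively.
2. Do not present the count rule as a coverage remedy (step 7). Name the prevalence interval. Report prevalence from a fixed sample, such as the first 1000 or first 3000, with its ordinary 95% interval beside the pooled estimate, or use an interval that allows for the stopping rule.

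**Cost.** Wording in three places and one extra line in the report. Screening would not end at 1000. The fixed-sample interval is wider than the pooled one: at ALK 4% the half-width 1.96 × √(0.04 × 0.96/n) is 1.2 points at 1000, 0.70 at 3000 and 0.50 at 6000. A stopping-adjusted interval takes more work and needs a fully defined rule for both genes, so the fixed-sample report is the simpler choice.

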4.2 STATISTICAL DECISION RULES

In case of multiple testing P values thresholds will be computed with Benjamini- Hoshberg criterion and $FDR \leq 0.05$. For other cases P value ≤ 0.05

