8 STATISTICAL METHODOLOGY AND STATISTICAL ANALYSES

8.1 STATISTICAL METHODS

a. Sample Size Calculation:

The sample size can be estimated according to a desired sensitivity or specificity, and the choice of the N obtained will be defined by privileging to maximize the sensitivity (cut-off value defined > 0.8). The sample size necessary to demonstrate hypothesis will be defined. This calculation will be made at each of the interim analysis, to evaluate the total number of patients to be recruited. The sample size calculation formulas are defined

Formula of the sample size calculation dependent on Sensitivity

$$N(sN) = \frac{TP+FN}{P}$$

Where,

$$TP+FN = z^2 \times \frac{(SN(1-SN))}{W^2}$$

TP : Prevalence of ALK rearrangements in the population and / or in the data set of the interim analysis.

SN : Minimal acceptable sensitivity

W : Desired confidence interval, also called α (here a 99 % is desired)

z : Constant dependent on the desired confidence interval, this value is obtained from the table of the normal distribution. For a 95 % confidence interval the value of z is 1.96, and for a range of 99 %, it is 2.58.

i. Formula of the calculation of the sample size dependent on the Specificity:

$$N(sP) = \frac{FP+TN}{(1-P)}$$

Where,

$$FP+TN = z^2 \times \frac{(SP(1-SP))}{W^2}$$

P : Prevalence of ALK rearrangements in the population and / or in the data set of the interim analysis.

SP : Minimal acceptable specificity

W : Desired confidence interval, also called α (here a 99 % is desired)

z : Constant dependent on the desired confidence interval, this value is obtained from the table of the normal distribution. For a 95 % confidence interval the value of z is 1.96, and for a range of 99 %, it is 2.58

b. Concordance test:

i. Test type:

The agreement between Ventana ALK and NGS assay for ALK will be evaluated based on the Binary Qualitative type (Two tails), where the results can only have two values (concordance, discordance). The following metrics will be evaluated from the results:

- *Sensitivity:* $\frac{TP}{(TP+FN)}$
- *Specificity:* $\frac{TN}{(TN+FP)}$

- *Precision: PPV* = $\frac{TP}{(TP+FP)}$
- *Accuracy*: $\frac{TP+TN}{TP+TN+FP+FN}$
- Limit of detection (LOD): They will be established a priori by the reference values delivered by Thermo Fisher. After the interim analysis, these will be re-evaluated and / or modified. Among the influential values in the limits of detection are: the coverage

ii. Concordance methods:

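### The interim sizing is described as securing power, but the SAP's only visible formula controls interval width and cannot secure power for any test

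*SAP*

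**What the plan says.** SAP section 3 gives the purpose of the second interim: "The main objective of this interim analysis is to determine the number of total recruited patients needed to get the statistical power". SAP 8.1a links the same calculation, repeated at each interim, to the hypothesis: "The sample size necessary to demonstrate hypothesis will be defined".

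The method offered for this is in SAP 8.1a, which begins "The sample size can be estimated according to a desired sensitivity or specificity". For sensitivity, the number of positives is z² × SN(1 − SN) / W², and this is divided by the ALK prevalence P to give the number screened. The inputs are described as follows:

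- Sensitivity entered: "SN : Minimal acceptable sensitivity", with the only numerical criterion given as "the choice of the N obtained will be defined by privileging to maximize the sensitivity (cut-off value defined > 0.8".
- Precision: "W : Desired confidence interval, also called α (here a 99 % is desired".
- Level: "For a 95 % confidence interval the value of z is 1.96, and for a range of 99 %, it is 2.58".

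The decision rule in SAP 4.2, outside multiple testing, is "For other cases P value ≤ 0.05". Protocol 7.4 describes its precision with a 95% interval. SAP 4.1 states that only the concordance aim has a tested hypothesis, namely equality of the NGS and Ventana ALK results. SAP 8.1b names McNemar's test and Cohen's kappa for it.

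**The concern.** A power calculation needs a null value, an alternative, a significance level, a target power and a named test. The formula in SAP 8.1a has a level and one sensitivity value, and that value is the minimum acceptable one. It answers how wide an interval will be. It does not answer how likely the study is to demonstrate anything.

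This calculation is meant to settle total recruitment, in a study that Protocol 7.4 allows to grow from 3000 to 6000 patients. If it is carried out as written, the study report could say that recruitment was set to secure power when no power had been calculated. Using different confidence levels for sizing, testing and reporting adds to the problem, because the number returned depends heavily on which level is used.

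**Working it through.** **Inputs.** From the SAP: SN = 0.8 (8.1a), z = 1.96 or 2.58 (8.1a), two-sided level 0.05 (4.2, 8.1b), ALK prevalence 3–5% (section 3). From Protocol 7.4: 120 ALK positives and 95% intervals. Assumed, because the visible text does not give them: half-width W = 0.10, true sensitivity 0.85 to 0.95, and a success rule (step 4).

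**1. The plan's own figure.** The visible SAP text gives no N to reproduce. The protocol's ALK target does reproduce as a case yield: 3000 × 0.04 = 120.

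**2. What the formula returns.** W is described as a confidence level, so it has no usable value. Taken literally with z = 2.58:

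- W = 0.99 gives 6.6564 × 0.16 / 0.9801 = 1.09 positives.
- W = 0.01 gives 6.6564 × 0.16 / 0.0001 = 10,650 positives.

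With W read as a half-width of 0.10:

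- z = 1.96: 3.8416 × 0.16 / 0.01 = 61.5, so 62 positives, or 61.47 / 0.04 = 1537 screened at 4% prevalence.
- z = 2.58: 6.6564 × 0.16 / 0.01 = 106.5, so 107 positives, or 106.50 / 0.04 = 2663 screened.

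The choice between 95% and 99% alone changes the requirement by a factor of 106.5 / 61.5 = 1.73.

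**3. Link to the planned test.** McNemar's test compares the two discordant proportions, and kappa measures agreement beyond chance. Neither tests sensitivity against 0.8, and neither the discordance rate nor an expected kappa enters the formula. The number it returns is therefore not derived from the hypothesis in SAP 4.1.

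**4. Power under an illustrative rule.** Let success mean that the two-sided 95% Wilson lower limit for positive percent agreement (PPA, which is sensitivity with Ventana as the reference) exceeds 0.80. The lower limit is [p + z²/2n − z√(p(1 − p)/n + z²/4n²)] / (1 + z²/n). For n = 120:

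- 105/120: (0.8750 + 0.0160 − 0.0613) / 1.0320 = 0.804, success.
- 104/120: (0.8667 + 0.0160 − 0.0629) / 1.0320 = 0.794, failure.

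Power is the exact binomial probability of 105 or more agreeing results out of 120. The same calculation for n = 107 has threshold 94.

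| True PPA | n = 107 (formula at 99%, W = 0.10) | n = 120 (protocol target) |
|---|---|---|
| 0.80 | 2.3% | 2.2% |
| 0.85 | 25% | 27% |
| 0.90 | 82% | 86% |
| 0.95 | 99.9% | >99% |

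In the first row the true value equals the one the formula plans at. The chance of showing more than 0.80 is then only the type I error, and no N improves it.

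**5. What a power calculation would ask for.** With null 0.80, two-sided 0.05 and 80% power, the normal approximation is N = [(1.96√(0.8 × 0.2) + 0.8416√(p(1 − p))) / (p − 0.8)]².

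- p = 0.90: [(0.7840 + 0.2525) / 0.10]² = 107.4, so 108 positives.
- p = 0.85: [(0.7840 + 0.3005) / 0.05]² = 470.5, so 471 positives.

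The answer depends on an expected sensitivity that the SAP formula has no place for.

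**The case against.** Several counter-arguments have force.

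- **No power level is stated, so none can be missed.** This stands. A reader might infer that a promised power is not delivered, or that the study is underpowered. The documents do not support either: there is no stated target to fall short of, and 120 ALK positives do well if agreement is 0.90 or more.
- **The re-assessments may contain the missing inputs.** SAP section 11 lists sample-size re-assessments as Appendices 4, 5, 7 and 8, and their content was not available. They may give a power, an expected sensitivity or a numeric W. The finding is therefore limited to the visible text. The body of the SAP should still be consistent with any such appendix, and SAP 8.1a does not point to one.
- **Planning at the minimum sensitivity is conservative.** For a precision formula this is correct. Above 0.5, a lower SN gives a larger n, so it is not an error in itself. It fails only when the result is presented as power to exceed that minimum.
- **Sizing at 99% and testing at 0.05 is also conservative, and 8.1a lists both z values.** This is true for adequacy, but the inconsistency still leaves the required number undetermined.
- **The 0.80 success rule is not in the SAP.** This is true. The 0.8 cut-off appears only in the sizing paragraph, so the power figures are an illustration and do not measure the planned analysis.

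**Conclusion.** The point holds in a limited form. SAP section 3 and 8.1a describe the interim sizing as a power calculation tied to the hypothesis, while the only formula shown fixes interval width, at the minimum acceptable sensitivity, with no connection to the planned test. Power is undefined in the visible text and is not secured by the method.

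Two sizes can be given. The disagreement over confidence level changes the required positives from 62 to 107 if W is 0.10, which is an assumed value. Under the assumed Wilson rule against 0.80, power at 120 evaluable ALK positives runs from about 27% to over 99% across true agreement of 0.85 to 0.95, so 120 is enough only if agreement is about 0.90 or higher. Both results treat the 120 as Ventana-positive samples that remain in the primary analysis. SAP section 7 removes samples such as those failing RNA quality control, so the evaluable count could be lower.

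**What to change.** Choose one of two routes and apply it in both SAP section 3 and 8.1a.

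- **(a) Precision.** Call the calculation precision-based and delete the references to power and to demonstrating the hypothesis. Define W as a numeric half-width, and use one level, 95%, to match SAP 4.2 and Protocol 7.4.
- **(b) Power.** Replace the formula with an exact binomial calculation for ALK PPA against the SAP's own 0.8 cut-off. State the expected PPA, use the two-sided 95% level throughout, and report power at the evaluable ALK-positive count. Make that criterion the stated decision rule, so that sizing and test agree.

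If the re-assessment appendices already state a power and an expected sensitivity, cite them in 8.1a and align the formula with them.

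The cost is SAP wording and a short calculation. Route (b) also adds a performance criterion that the SAP does not now test, which is a design decision for the sponsor, and the reported power may be unfavourable if expected agreement is below about 0.90.
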